***Other Supporting Measures (collected at baseline and 3 months unless otherwise indicated)***

**Medical events.** Will be collected at 3 months. Any responses will be reviewed by the study team to determine if a Serious Adverse Events report is required.

***Process and Adherence Measures (collected over 6 months)***

*Dietary Monitoring.* Engagement will be assessed via frequency of dietary monitoring. Each food entry will be time-stamped and automatically captured by the study website interface. Frequency of dietary monitoring will be defined as the total number of days during the 3-month intervention that participants tracked breakfast or lunch AND dinner, which will be considered a full (versus partial) day of tracking.

*PA monitoring.* Objective self-monitoring of PA will be assessed via the Fitbit tracker data for all groups. Data will be collected using the Fitbit application program interface (API). We will collect data on frequency and number of days that activity was tracked using the Fitbit (steps>500/day). These data will be tabulated to derive a measure of percent of days in which activity was tracked, and average activity tracking days per week. We will also ask participants how often they viewed the Fitbit website/mobile app to access graphs of their physical activity trends.

*Adherence to Dietary Goals.* Adherence will be measured as the total number of full days of tracking (i.e., breakfast or lunch AND dinner) during which participants met their dietary goal. Non-adherence will be assumed for partial days of tracking, or days where participants did not track.

*Engagement measures:* Using REDcap and study specific TLA website analytics we will examine website logins, goal setting, viewing feedback, lesson views, calculated as average logins and component views per week.

*Program Acceptability and Satisfaction.* Participants will be asked to complete a post-treatment program evaluation. Measures will be adapted from previous studies and assess intervention exposure and attention, perceived personal relevance, and satisfaction with intervention components.

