Physical activity recommendation. The ultimate goal for the study will be to progress the participant to at least 150 minutes of moderate to vigorous physical activity. The initial session and behavioral lesson materials will highlight both that the current physical activity guideline for cancer survivors is at least 150 minutes per week of moderate-to-vigorous PA (MVPA) minutes/week (i.e., 3-5 metabolic equivalents (METs) and the benefits of light PA (e.g., every 60-minute increase in light PA is associated with a 16% reduction in mortality). An initial goal will be based on baseline levels of activity as established during the baseline assessment for the study. Progression will occur each week based standard gradual physical activity plans we have previously used in distance-based intervention for YACS (LCCC1323, LCCC1709), and will be based on baseline PA activity levels and individual progress each week.

Dietary recommendations. The specific recommendations for diet composition are consistent with American Cancer Society and American Institute for Cancer Research nutrition guidelines for cancer survivors and the Traffic Light Approach (TLA) concept we have used in previous interventions. This intervention component will test a simplified dietary monitory approach that emphasizes ACS recommended dietary approaches: eating foods that help achieve and maintain a healthy body weight such as a variety of whole fruit and vegetables in a variety of colors, fiber-rich legumes, and whole grains, and limiting or excluding red and processed meats, sugar-sweetened beverages, highly processed foods and refined grain products, and alcohol.

Traffic Light Approach. To encourage long-term adherence to dietary monitoring, this study will use a simplified form of tracking based on the Traffic Light system. Rather than tracking calories as in traditional behavioral interventions, TLA is a simplified approach to dietary monitoring that categorizes food into colors of the stoplight based on their nutrient and calorie content. In the Traffic Light Approach, foods are categorized into green, yellow and red categories. Users are encouraged to increase green foods, moderate yellow foods, and limit red

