foods. Foods in the green category include fruits, vegetables, and certain very lean proteins, are low in calories, fat, and sugar and rich in nutrients. The high volume, water content and fiber in fruits and vegetables and the protein from the lean meats and egg whites in this category help promote satiety while consuming fewer calories. The yellow category includes moderately lean proteins, legumes, low fat dairy, whole grains, starchy vegetables, and low-fat dressings. These foods are higher in calories than green food but are still a good source of nutrients. Red foods are high in calories, fat, and/or sugar and are not a good source of nutrients. The goal in the Traffic Light Approach is to increase green foods and to limit red foods.

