## Description of Intervention Components (Factors)

In addition to the core intervention, participants will receive one level of each of four candidate intervention components to be evaluated: 1) simplified dietary tracking based on the Traffic Light Approach (daily tracking of green (low-calorie, high nutrients) vs. red (high-calorie, high-fat, low nutrients) foods), 2) dietary goals using Traffic Light Approach (daily green or red food goals vs. no goals), 3) supportive text messages (yes ( $\leq 5$  per week) vs. no), and 4) lesson delivery (all provided once vs. weekly).

*Candidate intervention components and their levels are described in detail below:*

**Simplified Dietary Tracking (green foods vs. red foods).** Self-monitoring has repeatedly been shown as an essential self-regulation strategy for physical activity and dietary behavior change success. However, traditional dietary self-monitoring is challenging and time-consuming and adherence to self-monitoring typically declines over time. The TLA might be more feasible and sustainable since participants only monitor a subset of foods reducing participant burden to engaging with self-monitoring behaviors.

Simplified dietary tracking using the TLA targets self-regulation through specific cognitive behavioral strategies including—reducing intake of certain foods (red foods), increasing intake of healthier choices (green foods), planning meals in advance, regular mealtimes, self-monitoring of foods, etc. Dietary approaches that promote increased fruit and vegetable intake can lead to improved diet quality and displacement of calorie-dense foods. Our previous interventions that used a simplified dietary monitoring approach based on the TLA have shown promise for promoting adherence to dietary goals and weight loss in young adults. However, no interventions have compared the effects of maximizing green food consumption or minimizing red food consumption on diet quality in young adults.

Participants will be randomized to use the TLA to either self-monitor their consumption of GREEN foods OR RED foods.

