## 6. DATA COLLECTION AND MANAGEMENT

### 7.

The rigorous system used for participant tracking, data collection, management, and quality control procedures for our previous projects (SNAP: U01HL090864; IMPACT: R01CA204965) will be modified for this study. All data will be entered using the REDCap computer-assisted program that has built-in validation checks for range, data type, and completeness. All measurements will undergo consistency and outlier checks, compared with raw data, and edited as required. REDCap includes detailed audit logs that document any database changes, and we will document protocols for cleaning data.

Participants will provide physical data (objective weight and self-reported height), self-reported questionnaire data online, and self-reported physical activity data over the telephone specifically for research purposes. All self-report online data will be collected using secure REDCap surveys. Food log data will be collected using CareEvolution's MyDataHelps™ mobile app. Data is securely stored in the HIPAA compliant, Meaningful Use Certified EDC HIEBus™ platform. CareEvolution® platforms comply with the security and privacy controls defined by NIST 800-53 Rev. 4 at the FISMA Moderate baseline. They regularly undergo external formal assessments by a FedRAMP-accredited Third Party Assessment Organization (3PAO). The platform has been granted an Authorization to Operate (ATO) by the National Institutes of Health (NIH) and is FDA Part 11 Compliant ([[contact]](mailto:[contact])). MyDataHelps integrates Fitbit using the Fitbit API.

Identifiable information collected in online surveys will include the participant's name, address, phone numbers, and date of birth.

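### The full-day tracking rule does not say how a meal with none of the assigned-colour foods counts; unless the log accepts a 'none' entry, tracking and goal adherence partly measure what was eaten

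*Combined protocol and SAP*

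**What the plan says.** Section 3, Process and Adherence Measures, defines two dietary measures.

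- **Tracking frequency** is the number of intervention days on which "participants tracked breakfast or lunch AND dinner, which will be considered a full (versus partial) day of tracking". The record behind it is described in one sentence: "Each food entry will be time-stamped and automatically captured by the study website interface".
- **Goal adherence** is the number of those full days on which the dietary goal was met. For all other days, "Non-adherence will be assumed for partial days of tracking, or days where participants did not track".

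Section 2, Simplified Dietary Tracking, restricts what is logged: "Participants will be randomized to use the TLA to either self-monitor their consumption of GREEN foods OR RED foods". The stated rationale is that the approach may be more sustainable "since participants only monitor a subset of foods reducing participant burden". A third colour belongs to neither log: "The yellow category includes moderately lean proteins, legumes, low fat dairy, whole grains, starchy vegetables, and low-fat dressings". The general advice is that "Users are encouraged to increase green foods, moderate yellow foods, and limit red" foods.

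Section 2, Nutrition Goals, sets an upper limit of 2 to 6 foods a day for the red group and a target of 6 to 12 a day for the green group. Both apply only to participants randomized to goals.

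The Synopsis makes dietary tracking by experimental condition a secondary objective. Section 4, Secondary Endpoint Analysis, summarises adherence to daily self-monitoring descriptively. Goal adherence is not named in either place.

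No section says how a meal with none of the assigned colour is recorded, or whether the log accepts a zero.

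**The concern.** A rule that requires entries at particular meals presumes that each such meal yields something to log. Colour-restricted logging removes that presumption. A lunch of legumes and whole grains is all yellow, so it gives nothing to log under either assignment.

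If food entries are the only record, a blank meal has two meanings: nothing of that colour was eaten, or the participant did not log. The tracking count then mixes logging behaviour with intake, and intake is what the green-versus-red factor is meant to change. For goal adherence, the red goal is a ceiling, so eating no red food is full success; yet the rule scores that day as failure. Blank meals cannot be separated into the two kinds after data collection.

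**Working it through.** The plan gives no figure for these measures, so there is nothing to reproduce. I applied its rules directly and then illustrated their size under stated assumptions.

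**Step 1. What the rule needs if only food entries count.** The wording allows two groupings:

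- A: (breakfast or lunch) and dinner. At least 2 entries, at two different meals.
- B: breakfast, or (lunch and dinner). At least 1 entry if it is at breakfast, otherwise 2.

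| Red foods that day | Meets a limit of 2 to 6? | Full day under A? | Full day under B? |
|---|---|---|---|
| 0 | Yes, always | Never | Never |
| 1 | Yes, always | Never | Only if eaten at breakfast |

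The zero-red result holds under both groupings. The one-red result is absolute only under A.

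Under A, ignoring snacks, the count patterns (breakfast plus lunch, dinner) within a limit L number (L+1)(L+2)/2, and those that are also full days number L(L−1)/2. For L = 2 that is 1 of 6; for L = 6 it is 15 of 28. These count patterns, not how often they occur.

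**Step 2. Cost per occurrence.** Lessons run weekly for 12 weeks (Section 2, Behavioral Lessons), so I take 12 × 7 = 84 days. One zero-red day a week costs a perfect logger 12/84 = 14.3 percentage points. Conditions 9 to 12 in Table 1 are red with goals. At 5 per cell (Section 4), that is 4 × 5 = 20 of 80 participants and 20 × 84 = 1,680 participant-days. One such day a week for everyone is 20 × 12 = 240 of these.

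**Step 3. Tracking frequency and intake (illustration).** Assume assigned-colour foods per day are Poisson with mean m, split equally over three meals, all logged. Then A = (1 − e^(−2m/3))(1 − e^(−m/3)) and B = 1 − e^(−m/3)[1 − (1 − e^(−m/3))²].

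| m | Full days, A | Full days, B |
|---|---|---|
| 1 | 13.8% | 34.1% |
| 2 | 35.8% | 60.8% |
| 4 | 68.5% | 87.9% |
| 6 | 84.9% | 96.6% |
| 12 | 98.1% | 99.9% |

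Logging is perfect in every row; only intake changes.

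**Step 4. Red days that meet the limit (illustration).** With the same Poisson count, the zero-red share of limit-meeting days is 1 / Σ m^j/j!, summed over j = 0 to L. For m = 1, L = 2 it is 1/2.5 = 40%. For m = 6, L = 6 it is 1/244.6 = 0.4%. Adding one-red days (grouping A) gives 2/2.5 = 80% and 7/244.6 = 2.9%.

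**Step 5. Green goal days (illustration, grouping A).** A goal-meeting green day has at least 6 entries, so the count alone never blocks it. Placement can. With a share b of foods at breakfast or lunch and d at dinner, the chance that a day of k foods is full is 1 − (1−b)^k − (1−d)^k + (1−b−d)^k. Take b = 0.50 and d = 0.25 (four equal occasions):

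- k = 6: 80.7% full, so 19.3% lost.
- k = 12: 96.8% full, so 3.2% lost.

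**Step 6. Direction (same formula).** The chance of a full day is 46.9% at 3 foods and 89.6% at 8. Eight red against three green favours red by 89.6 − 46.9 = 42.7 points; the reverse intakes favour green by the same amount.

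**Step 7. With a 'none' confirmation.** A perfect logger has 100% full days in either colour, and red adherence equals the share of days within the limit. In the Step 3 model with m = 2, a limit of 4 and grouping A, that is 94.7%, against 31.2% when only food entries count.

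**The case against.** The strongest reply is that the harm depends on a log screen that the documents do not describe. Saying that entries are time-stamped does not say that they are the only record, and a rule written by meal would suit a log with meal-level completion. This stands: a reader might infer that the log lacks a 'none' entry and that the measure is therefore biased, but the documents show only that the rule is unstated. The point has to stay conditional.

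Three further limits also stand.

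- A reader might infer that only red participants are affected. Step 5 shows otherwise: green goal days pass through the same full-day rule.
- A reader might infer that 0 or 1 assigned food can never make a full day. That holds for zero; for one food it depends on the grouping, which the wording leaves open.
- The illustrative percentages rest on assumed intakes and meal splits. They also vary the mean and the limit separately, although the plan sets limits from baseline intake.

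It is also fair that the stakes are modest. The planned mixed models cover MVPA, HEI and other secondary measures, not tracking adherence, and the limitations paragraph in Section 4 already warns that effect sizes may be inconclusive for choosing components.

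What does not stand is treating this as a mere omission of detail. Taken literally, the rule returns the wrong adherence result for a zero-red day, and the lost information cannot be recovered later.

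**Conclusion.** The point holds in conditional form. Unless the log accepts a 'none' entry, full-day tracking depends on intake in both arms, and a zero-red day that meets every permitted limit is scored non-adherent under either grouping. A one-red day is also blocked if the rule means (breakfast or lunch) and dinner. The goal-adherence effect is stronger for red with goals (conditions 9 to 12) but not exclusive to it.

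The size that follows from the rule is 14.3 percentage points for each zero-red day per week in a perfect logger, taking 84 intervention days. The overall size is unknown, because the documents give no intake distribution. For the same reason they do not support a claim that the rule favours one colour in the tracking comparison; Step 6 shows that either sign is possible.

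The affected measures are a descriptive secondary objective and a process measure. The definition should be settled before the data are collected, but the point does not touch the participation, accrual or retention endpoints, HEI or MVPA.

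**What to change.** In Section 3, Process and Adherence Measures:

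1. Define a tracked meal, in both colour arms, as one with at least one assigned-food entry or an explicit confirmation that none of the assigned foods was eaten at that meal.
2. Keep the full-day rule on that basis, and state which grouping of the meals is meant.
3. Score goal adherence on the day total of full days so defined. Confirmed zero-red days then count as meeting the limit, and incomplete logs still do not.

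If the log already records 'none', one sentence saying that it counts as tracked is enough. If it cannot, state that green-versus-red differences in entry-based tracking and goal adherence will not be interpreted as a component effect.

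As a separate point of wording, name the system that supplies the entries. This section says the study website interface, whereas Section 6 says "Food log data will be collected using" a mobile app.

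The cost is a short definition, slightly more participant burden, and possibly a small change to the app log. The app is a third party's, and the documents do not say how easily it can be changed. No goal, limit or other part of the intervention is altered.

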***Other Measures (collected at baseline, 6 weeks, and 3 months, unless otherwise indicated)***

*Medical events* and symptoms will be collected at 6 weeks and 3 months in a self-report questionnaire. Responses will be reviewed to determine if follow up is necessary with a scheduled telephone call, and if a Serious Adverse Events form is required.

*Demographics.* At baseline, standard demographic information will be collected

*Medical history, Medication use.* Self-report of both prescription and non-prescription medications.

*Smoking, alcohol use.* Smoking and alcohol use will be assessed at each time point.

## 4. STATISTICAL CONSIDERATIONS

### Sample Size and Power

The sample size is based on feasibility. Our primary feasibility measures are participation, accrual, and retention rates. Anticipated participation and retention rates are based on pilot feasibility studies among YACS and our previous work with this population. With an estimated participation rate of 85% (consistent with CO-I's experience, LCCC 1707), we anticipate it will be feasible to recruit 80 YACS within 6 months. We will test the null hypothesis that the proportion recruited is 50% or lower versus the alternative that it is 65% or greater using a one-tailed test at an alpha level of 0.05 with 95% power, which would support that the study is feasible.

We plan to accrue no more than 100 participants looking to have at least 80 evaluable participants, for 5 participants in each of the 16 groups. We expect accrual to take a total of 10 months at a rate of approximately 10 participants per month. We anticipate accruing 80 participants within 10 months, or 12-15 participants per month. A sample size of 80 achieves 99% power to detect a difference between a null hypothesis mean accrual rate of 12 participants/month and an alternative hypothesis mean of 15 participants/month with a significance level of 0.05 using a one-sided one-sample Poisson test.

For retention, we will test the null hypothesis that the retention is 70% or below versus the alternative that the retention is 90% or greater using a one-tailed test at a 0.05 alpha level. With 80 participants we would reject the null hypothesis that the retention is 70% if at least 62 participants are retained with 90% power, which would support that the study is feasible. With 80 participants we would reject the null hypothesis that the retention is 70% if at least 66 participants are retained with 97% power, which would support that the study is feasible.

All three endpoints must meet the proscribed criteria in order for the study to have successfully demonstrated feasibility.

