## 1.2 Name and Description of Investigational Intervention

The YACS HEAL (Young Adult Cancer Survivors Healthy Eating and Active Lifestyle) trial is a 2 full factorial experimental trial testing the efficacy of 4 intervention components (factors), each with two levels, to identify component levels that contribute to greater change in MVPA and diet quality among YACS. To do so, we will randomize 80 YAs with overweight or obesity to receive one level of each of the 4 intervention components, in addition to a core mobile-delivered behavioral physical activity and nutrition program.

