#### *Elements Common to All Experimental Conditions*

Core Intervention (n=80) all participants will receive a core intervention that includes PA and nutrition education modified from concepts of the Diabetes Prevention Program , our prior studies , and based around the consensus guideline recommendations for cancer survivors. Participants will be given digital tools to facilitate self-monitoring – a PA tracker and simplified diet tracking tool to support self-regulation of behaviors. The intervention will be delivered a mobile app integrated with Fitbit. Participants will receive an activity tracker (Fitbit) in the mail, followed by an introductory videochat session with an interventionist. In this session they will receive information relevant to their participation in the program, including an overview of how to use the study app (for both iOS and Android); Fitbit; the Traffic Light Log; how to self-monitor to achieve their daily goals (eating, activity, and self-weighing), and other information relevant to the conditions to which they have been randomized. Activity and dietary data are synced to study servers and activity is available in the app on pages that display participants' daily and overall progress towards their goals. The study app also includes 12 behavioral lessons that are delivered based on randomization. These include behavioral strategies with specific instruction on core cognitive and behavioral skills (i.e., goal setting, self-monitoring, problem solving, overcoming barriers, reaching out for social support, and cognitive restructuring).

Participants will receive qualitative feedback on self-monitoring behaviors and goal progress specific to MVPA and diet tracking (and goals). Feedback will include positive reinforcement and encouragement, strategies for barrier identification and overcoming barriers, and strategies for improving dietary and PA behaviors. Participants will receive tailored feedback summaries weekly. Participants will receive an email directing them to their feedback page. The feedback message will include feedback based on participants' number of days tracking diet and PA, and progress toward goals.

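### The plan uses 80 both as the number started and as the minimum number evaluable, so the sample size and the denominator of the retention cut-offs are undetermined

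*Combined protocol and SAP*

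**What the plan says.** The combined protocol and SAP uses 80 in three ways.

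- **As the number started.** Section 1.2 says "we will randomize 80 YAs with overweight or obesity". Section 2, under the elements common to all conditions, has "Core Intervention (n=80) all participants will receive a core intervention". Sample Size and Power adds "we anticipate it will be feasible to recruit 80 YACS within 6 months" and, later, "We anticipate accruing 80 participants within 10 months".
- **As the number left.** The same section says "We plan to accrue no more than 100 participants", and the sentence continues "looking to have at least 80 evaluable participants, for 5 participants in each of the 16 groups". The analytic plan in the synopsis also attaches n=80 to the 3-month evaluation.
- **As the denominator of a primary decision rule.** "With 80 participants we would reject the null hypothesis that the retention is 70% if at least 66 participants are retained", with a stated power of 97%. The sentence before it gives 62 as the count for the same hypotheses, with 90% power.

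The Statistical Analysis section defines the retention rate as those completing 3-month measures divided by those who consented. The synopsis lists 72 as the number of subjects without explanation. The missing-data section expects some attrition but gives no rate. Evaluable is not defined anywhere.

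**The concern.** A number started and a number remaining after follow-up normally differ by the attrition allowance. Here the same figure serves for both, and no attrition rate links the cap of 100 to the target of 80.

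Two things depend on which meaning is intended. One is the size of the data set for the 3-month component analyses and the within-condition change tests, for which 5 per condition is the stated basis. The other is the retention criterion. Retention is one of three primary feasibility endpoints, all of which must be met, and a count such as 62 or 66 has meaning only against a fixed denominator. If the number who consent is not 80, the printed counts are not the cut-offs for the test the plan describes.

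**Working it through.** **Inputs.** 16 conditions; 80 as used above; cap 100; retention null 70%, alternative 90%, one-sided alpha 0.05; retention = 3-month completers / consented. For this check, evaluable is taken to mean having 3-month data (an assumption).

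**Step 1: the plan's own figures.** 16 × 5 = 80 reproduces. For the retention rule, with X ~ Binomial(80, p), alpha = P(X ≥ c | p = 0.70) and power = P(X ≥ c | p = 0.90):

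| Cut-off c of 80 | Exact alpha | Exact power | Stated power |
|---|---|---|---|
| 62 | 0.087 | 0.9997 | 90% |
| 63 | 0.053 | 0.999 | – |
| 64 | 0.030 | 0.998 | – |
| 66 | 0.008 | 0.988 | 97% |

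The smallest count with exact alpha at or below 0.05 is 64. The normal approximation gives 80 × 0.70 + 1.645 × √(80 × 0.21) = 62.7, so 63, or 63.2, so 64, with continuity correction. Neither printed count is the 5% cut-off: 62 exceeds the stated alpha and 66 is much stricter than it. The 97% for 66 is within 2 points of the exact power; the 90% for 62 does not reproduce. This holds even if exactly 80 consent.

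**Step 2: suppose 80 start.** Expected completers = 80 × retention.

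| Retention | Completers | Per condition |
|---|---|---|
| 90% | 72 | 4.5 |
| 82.5% (66 of 80) | 66 | 4.1 |
| 77.5% (62 of 80) | 62 | 3.9 |

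The chance that all 80 complete at 90% retention is 0.9^80 = 0.0002.

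**Step 3: suppose 80 must complete.** Starters needed = 80 / retention, rounded up: 80/0.90 = 88.9, so 89; 80/0.80 = 100. Below 80% retention the cap is too small: 80/0.775 gives 104 and 80/0.70 gives 115. With 100 started, P(at least 80 complete) is 0.999 at 90% retention, 0.56 at 80% and 0.016 at 70%.

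**Step 4: the retention cut-off when more than 80 consent.** Smallest count with exact alpha ≤ 0.05 against 70%:

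| Consented | Cut-off | Exact alpha | Power at 90% |
|---|---|---|---|
| 80 | 64 | 0.030 | 0.998 |
| 89 | 70 | 0.045 | 0.9996 |
| 100 | 78 | 0.048 | 0.9999 |

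**Step 5: the synopsis figure.** 72 = 80 × 0.90, which would fit expected completers, but the document does not say so. As a number randomised it does not divide equally: 72/16 = 4.5.

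**The case against.** The strongest reply is that the plan can be read coherently. The Recruitment section puts consent first, then baseline assessments, then randomisation. Up to 100 consented, with 80 completing baseline and randomised 5 per condition, would fit section 1.2, section 2 and the cap, if evaluable means randomised with a complete baseline. That reading is open because the term is undefined, and it would remove the conflict over cell size. It does not rescue the retention counts: the stated denominator is those who consented, which on this reading could be as many as 100.

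Three stronger inferences are tempting and are not supported.

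- A reader might infer that 80 evaluable is impossible. It is not: with 100 started it is almost certain at 90% retention and slightly more likely than not at 80%. The 0.0002 in Step 2 applies only if the allowance above 80 goes unused.
- A reader might take 70% to 90% as a forecast, or the cap as a 20% loss allowance. The first two are the null and alternative values of a test; the third is a ceiling with no rate attached.
- A reader might infer a badly inflated false-positive rate. Applying the count of 66 to 89 or 100 starters would pass with probability 0.23 or 0.84 at a true retention of 70%. But the plan prints 66 for 80 participants, and its analysis section specifies a one-sample test of proportions. On the actual denominator that test would not reject at 66 of 89 (74.2%, exact p = 0.23) or at 66 of 100, which is below the null.

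It is also fair that the sample size rests on feasibility, with no precision target for the component effects, and that the limitations section concedes these may be inconclusive. A shortfall from 80 to 72 breaches no stated power for those effects.

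**Conclusion.** The point holds as an unresolved definition with a consequence for a primary criterion. If evaluable means having 3-month data, 80 cannot be both the number started and the number evaluable at retention of 90% or less: either about 72 are evaluable at 90%, or about 89 to 100 must start. In the second case, or whenever more than 80 consent, the counts printed for 80 are not the cut-offs for the retention rate as defined. Even with exactly 80 consented, the plan prints two counts and neither is the exact 5% cut-off of 64.

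The conclusion about cell size depends on the meaning given to evaluable; the conclusion about the retention counts rests on the plan's own definition of the rate. The effect is moderate: the evaluable number is 10% lower at 90% retention if 80 start, and the retention threshold moves between 64 and 78 completers according to how many consent.

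**What to change.** 1. State one number to be consented and one to be randomised, and use them in the synopsis, section 1.2, section 2 and Sample Size and Power. Reconcile the synopsis figure of 72 by saying what it counts.
2. Define evaluable.
3. Give the expected number of completers with its assumed retention. With 80 randomised, for example: 80 randomised, 5 per condition; about 72 expected with 3-month data at 90% retention. If 80 completers are wanted, state the number to start (89 at 90% retention, 100 at 80%).
4. Delete both retention counts (62 and 66). Replace them with a single exact one-sided 5% cut-off for the number who actually consent: 64 of 80, 70 of 89 or 78 of 100, with the exact alpha and power. If the intended denominator is those randomised, change the definition of the rate to match.

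The cost is wording. If 80 are randomised, the evaluable figure becomes slightly less favourable. No participants beyond the existing cap of 100 are needed.
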